14.0 Economic Burden to Subjects

14.1 Costs

No cost to subjects for participating.

14.2 Compensation for research-related injury

It is the policy of the institution to provide neither financial compensation nor free medical treatment for research-related injury. In the event of injury resulting from this research, medical treatment is available but will be provided at the usual charge. Such charges may be paid by the study sponsor as outlined in the research agreement and explained in the consent form.

15.0 Resources Available

15.1 Facilities and locations

The research will be conducted at the Penn State College of Medicine Department of Dermatology clinical trials unit.

15.2 Feasibility of recruiting the required number of subjects

There are over 1,200 patients with the diagnosis of hidradenitis suppurativa in the Penn State Health medical system. It is not possible to determine what number of these people have mild or moderate disease. We aim to recruit at least 18 total people, which is approximately 2% of the potential population of people with HS in the Penn State system.

15.3 PI Time devoted to conducting the research

PI has set amount of time each week indicated for research time only. [name] has 75% effort dedicated to research.

15.4 Availability of medical or psychological resources

Medical and psychological resources are available at the Penn State Milton S. Hershey Medical Center, at the same site as the clinical trial if needed.

15.5 Process for informing Study Team

All study team members will attend the SIV. If not available to attend they will be trained by reviewing the protocol and ICF. All training will be documented on a training log.

16.0 Other Approvals

16.1 Other Approvals from External Entities

Approval from the Penn State College of Medicine IRB and Incyte will be obtained prior to conducting the research.

16.2 Internal PSU Committee Approvals

Check all that apply:

- ☒ Anatomic Pathology – **Penn State Health only** – Research involves the collection of tissues or use of pathologic specimens. Upload a copy of “HRP-902 - Human Tissue For Research Form” in CATS IRB.
- ☐ Animal Care and Use – **All campuses** – Human research involves animals and humans or the use of human tissues in animals
- ☒ Biosafety – **All campuses** – Research involves biohazardous materials (human biological specimens in a PSU research lab, biological toxins, carcinogens, infectious agents, recombinant viruses or DNA or gene therapy).
- ☒ Clinical Laboratories – **Penn State Health only** – Collection, processing and/or storage of extra tubes of body fluid specimens for research purposes by the Clinical

Laboratories; and/or use of body fluids that had been collected for clinical purposes but are no longer needed for clinical use. Upload a copy of “HRP-901 - Human Body Fluids for Research Form” in CATS IRB.

- ☐ Clinical Research Center (CRC) Advisory Committee – **All campuses** – Research involves the use of CRC services in any way.
- ☒ Conflict of Interest Review – **All campuses** – Research has one or more of study team members indicated as having a financial interest.
- ☒ Radiation Safety – **Penn State Health only** – Research involves research-related radiation procedures. All research involving radiation procedures (standard of care and/or research-related) must upload a copy of “HRP-903 - Radiation Review Form” in CATS IRB.
- ☒ IND/IDE Audit – **All campuses** – Research in which the PSU researcher holds the IND or IDE or intends to hold the IND or IDE.
- ☐ Scientific Review – **Penn State Health only** – All investigator-written research studies requiring review by the convened IRB must provide documentation of scientific review with the IRB submission. The scientific review requirement may be fulfilled by one of the following: (1) external peer-review process; (2) department/institute scientific review committee; or (3) scientific review by the Clinical Research Center Advisory committee. NOTE: Review by the Penn State Health Cancer Institute (PSCI) Protocol Review Committee or the PSCI Disease Team is required if the study involves cancer prevention studies or cancer patients, records and/or tissues. For more information about this requirement see the IRB website.

17.0 Multi-Site Study

- 17.1 **Other sites**
Not applicable
- 17.2 **Communication Plans**
Not applicable
- 17.3 **Data Submission and Security Plan**
Not applicable
- 17.4 **Subject Enrollment**
Not applicable
- 17.5 **Reporting of Adverse Events and New Information**
Not applicable

17.6 Audit and Monitoring Plans
Not applicable

18.0 Adverse Event Reporting

18.1 Adverse Event Definitions

For drug studies, incorporate the following definitions into the below responses, as written:	
Adverse event	Any untoward medical occurrence associated with the use of the drug in humans, whether or not considered drug related
Adverse reaction	Any adverse event caused by a drug
Suspected adverse reaction	Any adverse event for which there is a reasonable possibility that the drug caused the adverse event. Suspected adverse reaction implies a lesser degree of certainty about causality than “adverse reaction”. 
 • Reasonable possibility. For the purpose of IND safety reporting, “reasonable possibility” means there is evidence to suggest a causal relationship between the drug and the adverse event.
Serious adverse event or Serious suspected adverse reaction	Serious adverse event or Serious suspected adverse reaction: An adverse event or suspected adverse reaction that in the view of either the investigator or sponsor, it results in any of the following outcomes: Death, a life-threatening adverse event, inpatient hospitalization or prolongation of existing hospitalization, a persistent or significant incapacity or substantial disruption of the ability to conduct normal life functions, or a congenital anomaly/birth defect. Important medical events that may not result in death, be life-threatening, or require hospitalization may be considered serious when, based upon appropriate medical judgment, they may jeopardize the patient or subject and may require medical or surgical intervention to prevent one of the outcomes listed in this definition.
Life-threatening adverse event or life-threatening suspected adverse reaction	An adverse event or suspected adverse reaction is considered “life-threatening” if, in the view of either the Investigator (i.e., the study site principal investigator) or Sponsor, its occurrence places the patient or research subject at immediate risk of death. It does not include an adverse event or suspected adverse reaction that had it occurred in a more severe form, might have caused death.
Unexpected adverse event or Unexpected suspected adverse reaction.	An adverse event or suspected adverse reaction is considered “unexpected” if it is not listed in the investigator brochure, general investigational plan, clinical protocol, or elsewhere in the current IND application; or is not listed at the specificity or severity that has been previously observed and/or specified.

18.2 Recording and Reporting of Adverse Events

Research subjects will be routinely questioned about adverse events at study visits. All adverse events (serious or non-serious) and abnormal test findings observed or reported to study team believed to be associated with the study drug(s) or device(s) will be followed until the event (or its sequelae) or the abnormal test finding resolves or stabilizes at a level acceptable to the investigator. Adverse events will be monitored from the time the participant signs the ICF up until the end of the 24-week study period. Adverse events (including laboratory abnormalities that constitute AEs) will be described using a diagnosis whenever possible rather than by underlying signs and symptoms.

An abnormal test finding will be classified as an adverse event if one or more of the following criteria are met:

- The test finding is accompanied by clinical symptoms
- The test finding necessitates additional diagnostic evaluation(s) or medical/surgical intervention; including significant additional concomitant drug treatment or other therapy
- The test finding leads to a change in study drug dosing or discontinuation of subject participation in the clinical research study
- The test finding is considered an adverse event by the investigator.

SAE Reporting to Incyte

The Principal Investigator (PI) must report all Serious Adverse Events (SAEs) to Incyte within 24 hours of learning of an event, regardless of the PI's causality assessment. This notification should be provided on a completed Serious Adverse Event (SAE) form. SAE reporting for each subject begins the day the informed consent is signed by the patient and within 30 days after subject has completed or discontinued from the study or has taken last dose of the study drug, or as described in the protocol.

SAEs, occurring using Incyte study drug, are reported in accordance with the effective protocol. SAEs occurring with any other commercial drug are reported to the manufacturer of that drug in accordance with regulations and protocol.

Initial SAEs and/or subsequent follow-up reports should be reported via email to [contact] or fax [name]. SAE reports should be for a single subject. SAE forms should be sent with a cover sheet and any additional attachments.

All adverse event information is reported to Incyte on the Principal Investigator's/Institution's Adverse Event Report Form, or a CIOMS-I or MedWatch Form FDA 3500A, or on an Adverse Event Report Form which may be provided by Incyte upon request. The Principal Investigator does not provide medical records (e.g., discharge summary) to Incyte, unless specifically requested.

Specifically, if there is a pregnancy during the study, an “Initial Pregnancy Report” or equivalent must be completed in full and emailed to [contact] or faxed to [name] within 24 hours of discovery of a pregnancy of a subject who has taken the Incyte product or the pregnancy of a partner for a subject who has taken the Incyte product. The “Follow-up Pregnancy Report Form” or equivalent must be completed and emailed to [contact] or faxed to [name] within 30 days after delivery, so that Incyte is provided with information regarding the outcome of the pregnancy. If the pregnancy results in any events which meet the serious criteria (i.e., miscarriage or termination), the SAE reporting process needs to be followed and the timelines associated with a SAE should be followed.

Guidelines for Interrupting, Restarting, and Discontinuing Study Drug in the event of an adverse event possibly related to the use of the ruxolitinib cream

ADVERSE EVENT	ACTION TAKEN
AST and/or ALT $> 3.0 \times \text{ULN}$	Subject will no longer be on study drug. Unscheduled blood draws will be completed, at intervals determined by PI, until lab values return to $\leq 3.0 \times \text{ULN}$
AST and/or ALT $> 5.0 \times \text{ULN}$	Subject will no longer be on study drug. Unscheduled blood draws will be completed at intervals determined by PI.
Platelet counts 50 to $< 100 \times 10^9/\text{L}$ or $\geq 50\%$ decrease from baseline	Subject will no longer be on study drug. Unscheduled blood draws will be completed, at intervals determined by PI, until the toxicity has resolved to $\geq 100 \times 10^9/\text{L}$.
ANC 0.5 to $< 1.0 \times 10^9/\text{L}$	Subject will no longer be on study drug. Unscheduled blood draws will be completed, at intervals determined by PI, until the toxicity has resolved to $\geq 1 \times 10^9/\text{L}$ or the baseline value.
Hemoglobin 8 to $< 10 \text{ g/dL}$ or $> 2 \text{ g/dL}$ decrease from baseline	Subject will no longer be on study drug. Unscheduled blood draws will be completed, at intervals determined by PI, until the toxicity has resolved $\geq 10 \text{ g/dL}$ or $\leq 2 \text{ g/dL}$ decrease from baseline.
Platelet count $< 50 \times 10^9/\text{L}$ ANC $< 0.5 \times 10^9/\text{L}$ ANC $< 1.0 \times 10^9/\text{L}$ with an oral temperature of at least 38.5°C OR with $\geq \text{Grade 3}$ infection Hemoglobin $< 8 \text{ g/dL}$	Subject will no longer be on study drug. Unscheduled blood draws will be completed, at intervals determined by PI.
Other adverse events that could be related to study drug use	
Any Grade 1 or Grade 2 severity	The subject will no longer be on study drug. At the discretion of the PI, unscheduled blood draws may be completed to monitor.
Any Grade 3 severity except those defined in Error! Reference source	Subject will no longer be on study drug. Unscheduled blood draws will be completed, at intervals determined by PI, until severity resolves to $\leq \text{Grade 1}$.

not found. (exception for any \geq Grade 3 nonhematologic severity)	
Any other Grade 4 severity	Subject will no longer be on study drug. Unscheduled blood draws will be completed, at intervals determined by PI.

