7.2 Study Procedures**7.2.1 Screening visit**

Informed consent	Laboratory screening obtained* 
 • Hepatitis B and Hepatitis C surface and core antibodies • Interferon-releasing assay for tuberculosis (or chest x-ray for those with a history of positive PPD) • Complete blood count (CBC) with differential • Hepatic panel (AST, ALT, Alk phos) • Fasting lipid panel (total, high-density, and low density cholesterol and triglycerides) • Pregnancy testing for women of child bearing potential (WOCBP)**
Inclusion/exclusion criteria reviewed	
Complete physical exam	
Clinician assessments (Lesion count, Hurley stage, HASI)	
Clinical photography of all lesions (do not include face)- kept in research files	
ECG	
Alcohol intake and recreational drug use	
Begin weekly surveys (more details below)	

*All blood will be obtained at Penn State Health outpatient laboratory.

**If subjects are postmenopausal, (defined as amenorrhea at least 12 months before screening) this will be confirmed by FSH levels drawn at the clinical site (approx. 2 teaspoons of blood)

Begin weekly surveys – These will be completed by the participants weekly through the end of Week 16 through REDCap. The weekly instruments will include patient-reported measures: NRS pain with 24-hour recall, NRS pain with 7-day recall, Hidradenitis suppurativa Quality of Life instrument (HiSQOL); medication use (assessing use of rescue medications or other potentially modifying medications or interventions).

7.2.2 Week 0, Baseline visit (28 ±5 days)- Can be combined with Screening Visit

Subjects will have a combined Screening/Baseline visit if all Inclusion/Exclusion criteria is met at the Screening visit.

Complete physical exam	Patient reported measures- collected electronically
------------------------	---

Clinician reported measures collected	WOCBP only- urine sample for pregnancy
Clinical photography	Dispense and start treatment with topical ruxolitinib 1.5% cream. Study coordinator will provide instructions for twice daily application.
Target lesion evaluated	Tissue sample collected (details below)

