7.2.5 Week 16/Early Termination (± 5 days)

Clinical photography	Laboratory Testing (approx. 8 tsp blood):
Complete physical exam	
 • CBC with differential • Hepatic panel (AST, ALT, Alk phos) • Fasting lipid panel (Total, high-density, and low density cholesterol, and triglycerides) • WOCBP only- urine sample for pregnancy
Patient reported measures-completed electronically	
Clinician reported measures	
Tissue sample collected (details below)	
Target lesion evaluated	
All dispensed medication (used and unused) will be returned to the research office	

Tissue sample of Target lesion identified at the baseline visit (whether active or resolved): We will collect a full-thickness skin punch biopsy (4-6mm) from the target lesion.

For all full-thickness skin punch biopsies, skin punch will be immediately placed in sterile specimen cup and transported on ice to [name] laboratory (C7801 BMR) for storage and analysis.

Biopsy will be bisected and portions will be formalin-fixed paraffin-embedded for planned immunohistochemistry analyses.

Remaining biopsy portion will be placed in RNALater and stored at -80C. Total RNA will be isolated from the skin punch and may be subjected to RNA-sequencing in future studies.

7.2.6 F/U Telephone Call (30 days post last dose of study medication) (+7 days)

Coordinator will call participant and discuss any new A/E's or changes in medication since the last dose of study medication.

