7.3 Duration of Participation

During the study, participants will have scheduled visits in the Dermatology Research Office at Screening, Baseline/Week 0 (can be combined with Screening), Week 4, Week 8, and Week 16. Each of these visits is expected to last for up to 60 minutes.

Participation will be up to 24 weeks long, including the screening and follow up periods.

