9.4 Frequency of data collection

Adverse events will be monitored at study visits from the time the participant signs the informed consent form up until the end of the study period. Study visits will occur at Screening, Baseline (Week 0), 4, 8, and 16. If there is a potential clinically significant abnormality in laboratory assessments, then an unscheduled visit the following week will be scheduled to repeat laboratory assessments is required.

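### With separate Screening and Baseline visits the schedule runs 170 days nominally and up to 187, so the 24-week (168-day) limit on participation and adverse-event monitoring can pass before the follow-up call

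*Combined protocol and SAP*

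**What the plan says.** Section 18.2 fixes the adverse-event window: "Adverse events will be monitored from the time the participant signs the ICF up until the end of the 24-week study period". Section 7.3 explains what the 24 weeks cover: "Participation will be up to 24 weeks long, including the screening and follow up periods".

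The schedule is in Section 7.2:

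- 7.2.2 places Baseline relative to Screening: "Week 0, Baseline visit (28 ±5 days)- Can be combined with Screening Visit".
- 7.2.5 puts a window on the end of treatment: "Week 16/Early Termination (± 5 days". All dispensed medication is returned at this visit.
- 7.2.6 adds a safety contact: "F/U Telephone Call (30 days post last dose of study medication) (+7 days". Its purpose is stated: "Coordinator will call participant and discuss any new A/E's or changes in medication since the last dose of study medication".

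Sections 9.3 and 9.4 describe the same adverse-event window without a number of weeks. Section 9.4 reads: "Adverse events will be monitored at study visits from the time the participant signs the informed consent form up until the end of the study" and so on, then lists the visits from Screening to Week 16. The telephone call is not in that list.

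Serious adverse events have their own rule in 18.2, which runs to 30 days after completion, discontinuation or last dose.

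**The concern.** The end of general adverse-event monitoring is a fixed number of weeks counted from consent. The follow-up call, serious-event reporting (18.2) and the recording of medications (7.4.6.5) are tied to the last dose. If the fixed number is smaller than the sum of the schedule's own intervals, the two kinds of rule conflict. A coordinator who hears during a planned call about a non-serious event that began on, say, day 175 has one section asking for it and another saying that monitoring is over.

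Two things are at stake. One is consistent handling of late non-serious events in a trial of roughly 18 to 24 people. The other is the accuracy of the stated maximum length of participation.

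**Working it through.** **Inputs**, with day 0 as the Screening visit at which consent is signed:

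- Stated limit (7.3, 18.2): 24 × 7 = 168 days.
- Screening to Baseline (7.2.2): 28 days, range 23 to 33; or 0 if the visits are combined.
- Baseline to Week 16 (7.2.5): 16 × 7 = 112 days, range 107 to 117.
- Last dose to call (7.2.6): 30 days, up to 37.
- Assumption: the last dose falls on the Week 16 visit day, when medication is returned.

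**The plan's own figure.** The documents do not show how 24 weeks was reached. It can be rebuilt as 4 + 16 + 4 weeks, that is 28 + 112 + 28 = 168 days, if the 30-day follow-up is rounded down to 4 weeks and all windows are ignored.

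**Check.** Day of call = screening interval + treatment interval + follow-up interval. Excess = day of call − 168.

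| Case | Sum | Day of call | Weeks | Excess over 168 |
|---|---|---|---|---|
| Separate visits, nominal | 28 + 112 + 30 | 170 | 24.3 | +2 |
| Separate, visits latest, call at 30 days | 33 + 117 + 30 | 180 | 25.7 | +12 |
| Separate, all windows latest | 33 + 117 + 37 | 187 | 26.7 | +19 |
| Separate, all windows earliest | 23 + 107 + 30 | 160 | 22.9 | −8 |
| Combined visits, nominal | 0 + 112 + 30 | 142 | 20.3 | −26 |
| Combined visits, latest | 0 + 117 + 37 | 154 | 22.0 | −14 |

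**How easily the limit is passed.** With Week 16 on time and the call at 30 days, the limit is met exactly at a screening interval of 168 − 112 − 30 = 26 days. Intervals of 27 to 33 days exceed it, which is 7 of the 11 days that the window permits. With Week 16 on time and the call at 37 days, even the shortest separate screening exceeds it: 23 + 112 + 37 = 172.

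**Sensitivity to the last-dose assumption.** If the last dose is one day before the visit, the nominal total is 28 + 111 + 30 = 169 days, still over. If it is two days before, the total is 168 and the nominal excess disappears. The latest-window total is then 33 + 115 + 37 = 185, which remains 17 days over.

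**The case against.** The strongest reply is that 24 weeks is a rounded label and was never meant as a cut-off on day 168. Much of this stands:

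- Section 7.3 counts follow-up inside the 24 weeks, so the period in 18.2 was probably meant to run through the call. Sections 9.3 and 9.4 attach no number to it.
- The nominal excess is 2 days, which is what rounding 30 days to 4 weeks would produce.
- Section 7.2.2 has participants who meet all criteria at Screening take the combined visit, and that route always fits. The documents do not say how many will have separate visits.

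A reader might go further and infer that safety follow-up can close 18 days after the last dose (168 − 150 in the latest-window case), or that post-dose observation differs between participants according to how long screening took. The documents do not support that:

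- The call is tied to the last dose for everyone and asks about events since then.
- Nothing instructs staff to discard what they hear after day 168.
- Section 9.7 defines treatment-emergent events by their start, with no end date, and its listings keep events whatever their timing.
- Serious events are covered by the separate 30-day rule.

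The reply does not rescue the number itself. Section 7.3 presents it as an upper limit, and a participant exactly on schedule with separate visits exceeds it. Section 18.2 then repeats it in a working safety rule.

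**Conclusion.** The inconsistency is real and minor. With separate Screening and Baseline visits, the stated maximum of 168 days is 2 days short at nominal timing and 19 days short at the latest windows. Taken literally, 18.2 ends adverse-event monitoring before the planned call by those same margins. Participants with combined visits, or with separate visits at the early ends of the windows, are unaffected.

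The figures assume that consent is signed at the Screening visit and that the last dose is on the Week 16 visit day. The 2-day nominal excess is sensitive to the second assumption; the excess at the latest windows is not. What remains is an unclear rule for non-serious events reported late in follow-up. No lost data, no biased safety table and no effect on the efficacy analysis has been shown.

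**What to change.** - **18.2:** end adverse-event monitoring at completion of the follow-up call (30 days, +7, after the last dose) instead of at a fixed 24 weeks.
- **9.3 and 9.4:** use the same end point, and add the telephone call to the contacts at which adverse events are collected.
- **7.3:** restate the maximum participation as about 27 weeks (187 days).
- **Participant-facing text:** update it if it repeats the 24-week figure. Those pages are not available here, so this part is conditional.

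The cost is a few wording changes in four sections, plus any matching participant text. The call is already planned, so there is no extra contact, and no treatment rule changes.
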